at least 90% power (because the detectable difference is big) and testing at 5% significance level. Based on these assumptions and using the method of Blackwelder for precision-based sample size calculations, a total of 20 participants per arm would be needed for arm 3 to test against each of arms 1 and 2 separately because the anticipated difference is too big. However, for arms 1 and 2 (Table 1 below), we will need more participants per group because a smaller detectable effect is anticipated. Using the Fisher's exact test power simulations, a difference in serologic response of 30% (say 50% vs 80%) gives more than 80% power (i.e. 85% power) with a sample size of 50 participants in each of arms 1 and 2 testing at 5% significance level. Therefore, the total sample size for all the 3 arms will be 120 participants. The size of study groups is relatively small hence it is imperative to minimise potential losses. Whenever possible an attempt will be made to replace study participants should a participant be withdrawn or choose to withdraw. The stata command for obtaining the Fishers exact test power simulations is: power two proportions 0.50 0.80, test (fisher) n1(50) n2(50). This has been performed in Stata 16. The required sample sizes are summarized as follows:

Table 1. Sample size and vaccine vials required for each arm

Group	# Participants	Vaccine	Dose M0	Dose M1	Dose M2	Vaccine vials required
1	50	R21/Matrix-M™	Single standard dose (0.75mL)	Single standard dose (0.75mL)	Single standard dose (0.75mL)	300
2	50	R21/Matrix-M™	Single standard dose (0.75mL)	Single standard dose (0.75mL)	Single standard dose (0.75mL)	300
3	20	No vaccine	No vaccine	No vaccine	No vaccine	0
Total	120					600

Remark: R21/Matrix-M™ = adult formulation containing 10 µg of R21 and 50 µg Matrix-M in the standard dose of 0.75mL.

B5.4 Recruitment Methods

Volunteers will be recruited using methods previously successfully employed by the Clinical Therapeutics Unit (CTU) of the Mahidol-Oxford Tropical Medicine Research Unit. The volunteer unit maintains a register of candidates who expressed interest in the past to participate in clinical trials. In addition, volunteers will be recruited via flyers.

For Group 1, 10 volunteers will be enrolled into the study and receive the first vaccination.

Safety report will be submit to FTMEC. If there is no safety concern which related to the study procedure, then the recruitment of the remaining volunteers will be continued.

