Participants withdrawn from the study agent are those who do not receive the complete number of vaccine doses. A participant withdrawn from the study agent may not necessarily be withdrawn from the study, as further procedures or follow-up may be performed (safety or immunogenicity), if planned in the study protocol. Information relative to premature discontinuation of the study agent will be documented in the CRF. The investigator will document whether the decision to discontinue further vaccination was made by the participant or the investigator and which of the following possible reasons was responsible for withdrawal:

- serious adverse event,
- non-serious adverse event,
- other (specify).

Research Proposal Submission Form for a study involving human subject enrollment WITH specimen collection

Document No.: FTM ECF-033-01

Page 14 of 52

Subjects with positive malaria tests on vaccination days at Month 1 or Month 2 will be treated according to national guidelines and the volunteer will be withdrawn from further vaccination.

B5.6 Indications for deferral of vaccination

The following events constitute contraindications to administration of R21/Matrix-M™ at that point in time. If any one of these adverse events (AEs) occurs at the time scheduled for vaccination, the participant may be vaccinated at a later date, or withdrawn at the discretion of the investigator.

Acute disease at the time of vaccination (acute disease is defined as the presence of a moderate or severe illness with or without fever). All vaccines can be administered to persons with a minor illness such as diarrhoea, mild upper respiratory infection with or without low-grade febrile illness, i.e. Axillary temperature <37.5°C).

- Axillary temperature of $\geq 37.5^{\circ}\text{C}$ at time of vaccination.
- Administration of a vaccine not foreseen by the study protocol within 7 days of any dose of R21/Matrix-M™ with the exception of vaccines against polio, diphtheria, tetanus, pertussis, hepatitis B, Haemophilus influenzae type b (Hib), Bacillus Calmette–Guérin (BCG vaccine), measles, influenza, pneumococcal disease, or yellow fever which may not be given within one week of vaccination.
- COVID-19 vaccines should not be administered 7 days before or after administration of the study vaccine due to potential adverse events e.g. fever.

B5.7 Absolute contraindications to further vaccination

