specimen collection**

Document No.: FTM ECF-033-01

Page 29 of 52

The investigators will permit authorized representatives of the sponsor, ethical committee(s), regulatory agencies, authorized individuals from, Jenner Institute and the monitors to examine (and when required by applicable law, to copy) clinical records for the purposes of quality assurance reviews, audits and evaluation of the study safety and progress.

B6.7 Data analysis

B6.7.1 Study Endpoints

We will assess the R21/Matrix-M™ recipients with regards to:

Safety: the occurrence of solicited and unsolicited AEs and SAEs (please see safety section)

Immunogenicity: (a) serum anti-CS IgG antibody titres responses to NANP and anti-CS antibody avidity, (b) cellular immunity.

B6.7.2 Inclusion in Analysis

All patients who received at least one dose of vaccine will be included in the safety analyses. Patients lost to follow-up before the completion of the follow-up period assessments will be censored at the last day seen.

B6.7.3 Immunology analyses

Given the incidence of malaria in the study area, it is highly unlikely that any volunteer will become infected with any Plasmodium species during the trial. However, to exclude the remote possibility that a participant becomes infected we will screen participants for malaria at screening, Month 0, Month 1, Month 2, Month 3, and Month 6. Participants positive for malaria at screening or Month 0 are excluded from participation in the study and will not be enrolled or vaccinated.

B6.7.4 Overall plan

Both intention-to-treat and per-protocol analyses will be carried out. In the intention-to-treat analysis, every participant randomized in the study (who receive the correct or incorrect study agent, one or more doses, and complete or incomplete doses) will be analysed, except if he/she did not receive any dose of the study vaccine or if no post-randomization data was collected for this participant.

The per-protocol analysis will compare participants according to the study agent actually received and will include only those participants who satisfied the inclusion/exclusion criteria, followed the protocol, and received three complete, correct doses. The following non-compliant participants will be excluded:

- Participants included without meeting at least one inclusion criterion
- Participants included despite meeting at least one exclusion criterion
- Participants found non-compliant with the blood sampling schedule

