**Research Proposal Submission Form
for a study involving human subject enrollment WITH
specimen collection**

Document No.: FTM ECF-033-01

Page 30 of 52

- Participants vaccinated with the wrong study agent (non-compliance with the randomization code)
- Participants excluded from the intention-to-treat analysis.
- No interim analysis is planned.

B6.7.5 Analysis of baseline characteristics

The demographic characteristics of enrolled participants will be compared by study group.

B6.7.6 Analysis of immunogenicity

The serum anti-CS antibody titre and avidity

The main analyses will involve the serum anti-CS antibody titre and avidity. These parameters will be measured at baseline and then at follow-up times longitudinally. During statistical analysis, we will assess whether a participant had a titre that is greater than 4 times that of the participant's baseline titre. Then we will compute the number of participants who had a titre of greater than 4 times their baseline titres and obtain a proportion of these for each group. These proportions of participants with >4-fold rise in titre from baseline will be compared between arms at each follow-up time. A Fisher's exact test will be used to compare the proportions of participants with >4-fold rise in titre from baseline between groups at each follow-up. These proportions will also be summarised graphically by arm to visually assess the differences between arms over-time. This will help to visually assess whether time modifies the effect of group.

Furthermore, the absolute titre values will be analysed and compared between groups. Since the distribution of these titre values will likely be highly skewed overtime, these values will be log-transformed and compared between arms at the different follow-up times. In order to revert back to the original scale (taking exponentials), the Geometric Mean Ratios (GMR) of the titres will be the measures of effect of interest that will be used to compared the log-transformed titres between the arms. The 95% confidence intervals for the Geometric Mean Ratios will be presented. The mean titre trends (on log-scale) over time will also be plotted by arm to assess whether there is a difference in trends of the titres between arms over time.

Tests of significance will be performed at 5% significance level. Analyses will be performed in Stata version 17 or higher. A separate detailed Statistical Analysis plan will be developed, finalized and signed before databased lock.

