4.1.4 ANALYSIS POPULATION

Primary outcome analyses will be carried out on both the according to protocol (PP) and the intention to treat (ITT) population. The PP analyses will be the main strategy for the immunogenicity analyses. The safety outcomes will be ITT. In the event of some subjects not meeting the in-/exclusion criteria at baseline being erroneously enrolled in the study, a modified intention to treat analysis (mITT) will be considered. In that case, reasons for exclusions will be clearly documented and justified. In the intention-to-treat analysis, every participant randomized in the study (who receive the correct or incorrect study agent, one or more doses, and complete or incomplete doses) will be analysed, except if he/she did not receive any dose of the study vaccine or if no post-randomization data was collected for this participant.

The per-protocol analysis will compare participants according to the study agent/treatment actually received and will include only those participants who satisfied the inclusion/exclusion criteria, followed the protocol, and received complete, correct doses. The following non-compliant participants will be excluded:

- Participants included without meeting at least one inclusion criterion
- Participants included despite meeting at least one exclusion criterion
- Participants found non-compliant with the blood sampling schedule
- Participants vaccinated with the wrong study agent (non-compliance with the randomization code)
- Participants excluded from the intention-to-treat (mITT) analysis.

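### The 85% power for Arm 1 v Arm 2 assumes 50 analysed per arm, but the main antibody analysis is per-protocol and the sample size has no inflation for exclusions

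*Protocol*

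**What the plan says.** Protocol B5.3, repeated in SAP 2.1.5, sizes the Arm 1 v Arm 2 comparison on the proportion with a four-fold antibody rise, taken as 50% v 80%. It says that this "gives more than 80% power (i.e. 85% power) with a sample size of 50 participants in each of arms 1 and 2". The Stata call, with its closing bracket left off here, is "power two proportions 0.50 0.80, test (fisher) n1(50) n2(50". The total of 120 is 50 + 50 + 20, with no percentage added. B5.3 recognises that losses matter and says that withdrawn participants will be replaced where possible.

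The planned test matches the power calculation. Protocol B6.7.6 states: "A Fisher's exact test will be used to compare the proportions of participants with >4-fold rise".

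The analysis set does not match it. SAP 4.1.4 states: "The PP analyses will be the main strategy for the immunogenicity analyses". Under Protocol B6.7.4 the per-protocol set is limited to participants who met the eligibility criteria, followed the protocol and "received three complete, correct doses". Both documents also exclude participants given the wrong agent and those who did not comply with the blood sampling schedule. SAP 3.1 further removes out-of-window results from the per-protocol style report, and removes immunology results obtained during and after parasitaemia. An intention-to-treat analysis is also planned.

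On stopping vaccine, Protocol B5.5 says: "A participant withdrawn from the study agent may not necessarily be withdrawn from the study". Neither document gives an expected per-protocol exclusion rate.

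**The concern.** The power is quoted for everyone randomised to the two vaccine arms, while the main antibody comparison will be run on a set that can only be the same size or smaller. Replacement is tied to withdrawal. A participant who stops dosing but remains in follow-up leaves the per-protocol set without necessarily counting as a withdrawal, and so does one who misses a sample.

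This comparison sets the size of the two vaccine arms. It also carries the stated aim of confirming that antimalarials do not reduce the response. If the result is not significant, readers will weigh it against the quoted 85%, so that figure should belong to the analysis being reported.

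**Working it through.** **Inputs.** From B5.3: response rates 0.50 and 0.80, 50 per arm, 5% level, Fisher's exact test. From B6.4.4: 5:5:2 allocation, so 1:1 for Arm 1 v Arm 2. Sidedness is not stated. Two-sided is assumed because it reproduces the 85%, whereas one-sided gives 91.7%. The exclusion rate is not in the documents, so a range of 0 to 20% is assumed.

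**Formula.** Power(n1, n2) = Σx Σy Bin(x; n1, 0.50) × Bin(y; n2, 0.80) × 1[Fisher p(x, y) ≤ 0.05], summed over every possible 2×2 table.

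**Step 1: the plan's own figure.** Power(50, 50) = 85.3%. The stated 85% is reproduced.

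**Step 2: equal losses in both arms.**

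| Per arm in the per-protocol set | Lost per arm | Fisher power |
|---|---|---|
| 50 | 0 | 85.3% |
| 47 | 3 (6%) | 83.0% |
| 45 | 5 (10%) | 81.5% |
| 44 | 6 (12%) | 80.2% |
| 43 | 7 (14%) | 79.6% |
| 40 | 10 (20%) | 74.9% |

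The plan's claim of power above 80% holds down to 44 per arm and fails at 43.

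**Step 3: unequal losses.** Fisher's test is discrete, so power does not fall steadily. With the 50% arm listed first: 49/50 gives 87.6%, 48/50 gives 85.5%, 50/45 gives 86.1%, 45/50 gives 84.6%, 40/50 gives 83.9% and 50/40 gives 83.2%.

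**Step 4: average over random exclusion.** Randomise 50 per arm and exclude each participant independently at rate q. Average power = Σa Σb Bin(a; 50, 1−q) × Bin(b; 50, 1−q) × Power(a, b).

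| Assumed exclusion rate q | Average Fisher power |
|---|---|
| 5% | 84.9% |
| 10% | 83.2% |
| 15% | 81.0% |
| 20% | 78.0% |

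**Step 5: how much of the 5% Fisher's test uses.** Setting both arms to a common rate p and maximising the rejection probability over p gives the true size. At 50 per arm the maximum is 3.5%; at p = 0.80 it is 2.8%.

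**Step 6: Boschloo's exact test.** Take the Fisher p-value as the statistic and choose the largest critical value for which the maximum rejection probability over p is at most 5%. The maximum size at 50 per arm is then 4.9%.

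| Per arm | Fisher | Boschloo | Gain (points) |
|---|---|---|---|
| 50 | 85.3% | 88.8% | 3.5 |
| 45 | 81.5% | 85.9% | 4.4 |
| 43 | 79.6% | 84.6% | 5.0 |
| 40 | 74.9% | 81.0% | 6.1 |

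**The case against.** The strongest reply is that nothing in the plan is miscalculated. The 85% reproduces, and no exclusion rate is given from which a shortfall could be asserted. A reader might infer that the 85% holds only if all 50 per arm are analysed, or that the main analysis certainly lacks it. The documents support neither reading. Some smaller unequal splits keep 85% (48/50, 50/45), and random exclusion of 10% costs about 2 points on average.

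A reader might also infer that the plan makes no provision for losses. It does provide for replacement. B5.3 does not say withdrawn from the study, and B5.5 also speaks of withdrawal from the study agent. B5.5 lets the investigator withdraw participants for ineligibility, significant deviation or non-compliance. Some per-protocol exclusions could therefore be replaced. But this is discretionary, attempted only where possible, and nothing ties it to the per-protocol exclusion list.

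Three smaller points stand in part. SAP 3.1 can be read as dropping only the out-of-window visit and not the participant. The intention-to-treat analysis keeps those with incomplete doses who have post-randomisation data. Geometric mean ratios with 95% confidence intervals will show the precision actually achieved. These limit the consequence, but SAP 4.1.4 still names per-protocol as the main strategy.

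Finally, Fisher's test is valid, prespecified and consistent with the power calculation. Its conservatism is not an error, and changing the test does not supply the missing exclusion assumption. That is fair. Boschloo's test is offered as a way to recover power within the same 5% limit, not as a correction of a mistake.

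**Conclusion.** The point holds in conditional form. The 85% is right for 50 analysed per arm; the main immunogenicity analysis may have fewer, and the plan neither inflates for that nor states the power at a smaller number. If exclusions are few, the effect is negligible: 84.9% on average at 5%. At 10% it is about 2 points. The plan's claim of power above 80% is lost at 43 per arm with equal losses, and on average somewhere between 15% and 20% random exclusion (81.0% and 78.0%).

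These figures rest on a two-sided test, true rates of 50% and 80%, an assumed exclusion rate, and exclusion unrelated to response. Exclusion that is related to response could also bias the comparison, which these figures do not cover.

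**What to change.** (a) In Protocol B5.3 and SAP 2.1.5, state that 85% applies if all 50 per arm are in the per-protocol set, and that Fisher power is about 82% at 45 and 75% at 40 per arm.

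(b) In Protocol B6.7.6 and the SAP section on immunogenicity analysis, prespecify Boschloo's exact test for the Arm 1 v Arm 2 responder comparison, and quote its power alongside: 88.8% at 50, 85.9% at 45 and 81.0% at 40 per arm, with size at or below 5%.

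The cost is wording in two documents, a slightly less favourable quoted Fisher power, and probably software other than the Stata named in B6.7.6 for one test. No extra participants are needed. By comparison, keeping 50 evaluable by inflation at an assumed 10% exclusion would take 50 / 0.90 = 55.6, so 56 per arm.

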Research Proposal Submission Form for a study involving human subject enrollment WITH specimen collection

Document No.: FTM ECF-033-01

Page 13 of 52

B5.5 Withdrawal/discontinuation criteria

Each participant has the right to withdraw from the study at any time and for any reason and is not obliged to give his or her reasons for doing so. Participants who are withdrawn because of AEs must be clearly distinguished from participants who are withdrawn for other reasons. For all withdrawals due to SAE/AEs, appropriate follow-up visits or medical care will be arranged, with the agreement of the participant, until the SAE/AE has resolved and stabilized

From an analysis perspective, a 'withdrawal' from the study is any participant who did not come back for the concluding visit or was not available for the concluding contact foreseen in the protocol. A participant qualifies as a 'withdrawal' from the study when no study procedure has occurred, no follow-up has been performed and no further information has been collected for this participant from the date of withdrawal/last contact. Investigators will make attempts to contact those participants who do not return for scheduled visits or follow-up.

In addition, participant may be withdrawn from the study by the investigator at any time, if it is in the best interests of the participant's health and well-being, or for any of the following reasons:

- Ineligibility (either arising during the study or retrospectively, having been overlooked at screening).
- Significant protocol deviation.
- Participant demonstrates significant non-compliance with study requirements
- An AE, which requires discontinuation of the study involvement or results in inability to continue to comply with study procedures.

If a participant withdraws from the study, blood samples collected before their withdrawal from the trial will be used/stored unless the participant specifically requests otherwise. Data collected prior to the withdrawal of a participant will be used. In all cases of participant withdrawal or discontinuation, excepting those of complete consent withdrawal, long-term safety data collection will continue as appropriate if subjects have received one or more vaccine doses.

Participant withdrawal from the study agent

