Vaccine and study medication accountability, storage, and handling will be in accordance with local SOPs. This study will not be blinded; i.e. it is an open-label study.

B6.2.2 Accountability of the study agents

The study site will maintain a record of the numbers of all vaccines and DHA/PIP + primaquine tablets obtained, used by the participants and returned to the pharmacy room in CTU. On study completion, a copy of the drug accountability record will be filed in the study folder.

B6.2.3 Concomitant medications

There will be no restrictions on concomitant medication beyond the exclusion criteria listed above.

B6.3 Study Endpoints

B6.3.1 Primary Endpoints

The safety of the investigational vaccine in each group:

- Occurrence of solicited from the date of each vaccination to 7 days of each vaccination.
- Occurrence of unsolicited adverse events (AEs) from the date of the first vaccination to 28 days after the last vaccination, according to the MedDRA classification.
- Occurrence of serious adverse events (SAEs) during the whole study period, i.e. during a 6-month follow up period from the receipt of first vaccination, according to the MedDRA classification.

B6.3.2 Secondary Endpoints

- For Arms 1 and 2, the concentration of antibodies against *Plasmodium falciparum* circumsporozoite (anti-NANP total IgG antibody), one month after the first dose (at Study month 1), one month after the second dose (at Study month 2), one month after the third dose (at Study Month 3) and six months after the first dose (at Study Month 6).
- Exploratory immunology endpoints including but not limited to cellular immunity.
- For Arms 1 and 3, piperaquine levels following the administration of the antimalarials with or without vaccine. (timepoints)

B6.4 Details of procedures for specimen/data collection

Procedures will be performed at the time points indicated in the schedule of procedures (Table 5). Additional procedures or laboratory tests may be performed, at the discretion of the investigators if clinically necessary (e.g. follow up repeat haematology or biochemistry laboratory tests in the event of clinically significant abnormal results).

Research Proposal Submission Form for a study involving human subject enrollment WITH specimen collection

Document No.: FTM ECF-033-01

Page 20 of 52

Table 5. Study Procedures

Timepoints	Month Day of month	Scr.	Study period																	
			M0				M1				M2				M3	M6 ^a				
			0 ^c	1	2	7	0	1	2	7	0	1	2	7	0	0				

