3.2 PRIMARY OUTCOME

The primary outcome measures will be:

- The safety of the investigational treatment in each group:
 - Occurrence of serious adverse events (SAEs) from the date of the first vaccination to 28 days after the last vaccination, according to the MedRA classification.
 - Occurrence of SAEs during the whole study period, i.e. during a 6 month follow up period from the receipt of first vaccination, according to the MedRA classification.
- For all the 3 groups, the concentration of antibodies against *Plasmodium falciparum* circumsporozoite (anti-CS antibody), one month after the first dose (at Study month 1), one month after the second dose (at Study month 2).

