- Frequency (%) of occurrence of unsolicited AEs from the date of the first vaccination to 28 days after the last vaccination, according to the Medical Dictionary for Regulatory Activities (MedDRA) classification with exact 95% CI, by group and severity.
- Frequency (%) of occurrence of SAEs (all, fatal, related to investigational vaccine) within 28 days (day of vaccination and 28 subsequent days) after each vaccination, according to the MedDRA classification with 95% CI.
- Frequency (%) of occurrence of SAEs (all, fatal, related to investigational vaccine) during the whole study period according to the MedDRA classification with exact 95% CI.
- Frequency (%) of occurrence of AEs and SAEs leading to withdrawal from further vaccination from Dose 1 (Day 0) up to study conclusion (Day 180), according to the MedDRA classification, for each vaccinated subject exact 95% CI.
- Frequency (%) of occurrence of pIMDs from Dose 1 (Day 0) up to study conclusion (Day 180), according to MedDRA classification, for each vaccinated subject with exact 95% CI.
- Frequency (%) of occurrence of meningitis from Dose 1 (Day 0) up to study conclusion (Day 180), according to the MedDRA classification, for each vaccinated subject exact 95% CI.

These will be summarised in table 4 below:

Table 4 Safety analysis

Safety parameter	R21/Matrix-M™ + DHA-PIP + SLD-PQ n=X	R21/Matrix-M™ n=X	No Vaccine n=X
Solicited local and general AEs within seven days n(%), (95% CI)			
Unsolicited AEs: date of 1 st vaccine to 28 days after last vaccine n(%), (95% CI)			
SAEs within 30 days after each vaccine n (%), (95% CI)			
SAEs for whole period n (%), (95% CI)			
AEs+SAEs leading to withdrawal from further vaccination from Dose 1 to study conclusion n(%), (95% CI)			
pIMDs from Dose 1 to study conclusion n(%), (95% CI)			

Biochemistry and haematological safety assessment.

Biochemistry (ALT, AST and creatinine) and haematological (haemoglobin, WBC, and platelets) laboratory values will be presented according to toxicity grading scales and tabulated by group. The normal ranges and toxicity grading for laboratory safety parameters those will be used in this study are in Appendix section (Table A1):

The following definitions will be used for clinical adverse events in this report: The intensity should be assigned to one of the following categories:

1 (mild) = An AE which is easily tolerated by the subject, causing minimal discomfort and not interfering with everyday activities.

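### Post-withdrawal safety collection is tied to vaccine receipt, so Arm 3 has no provision for new SAEs after leaving the study and whole-period ascertainment may differ by arm

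*Protocol*

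**What the plan says.** **The rule after withdrawal.** Protocol B5.5 opens the clause with "In all cases of participant withdrawal or discontinuation, excepting those of complete consent withdrawal" and then states that "long-term safety data collection will continue as appropriate if subjects have received one or more vaccine doses". It gives no duration or contact schedule for this collection.

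**Provisions not tied to vaccine.** The same section adds "For all withdrawals due to SAE/AEs, appropriate follow-up visits or medical care will be arranged, with the agreement of the participant", until the event settles, and "Investigators will make attempts to contact those participants who do not return for scheduled visits or follow-up". Both apply to every arm.

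**Stopping the study agent.** B5.5 treats this as separate from leaving the study, but defines it by vaccine alone: "Participants withdrawn from the study agent are those who do not receive the complete number of vaccine doses". Antimalarial rounds are not mentioned.

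**The endpoint.** Protocol B6.3.1 lists "Occurrence of serious adverse events (SAEs) during the whole study period" as a primary endpoint, under a lead-in that refers to each group. SAP 3.2 introduces the same outcome with "The safety of the investigational treatment in each group". Both start the six-month clock at the first vaccination. SAP section 5, Table 4 (Safety analysis) has a whole-period SAE row and a No Vaccine column.

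**The safety set.** Protocol B6.7.2 and SAP 3.1 base the safety analyses on vaccine recipients. SAP section 5 opens by limiting them to participants assigned to vaccine. SAP 4.1.4 makes safety an ITT analysis, and there and in protocol B6.7.4 the ITT definition drops anyone who had no vaccine dose.

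**The concern.** Arm 3 gets three rounds of antimalarials and no vaccine, so the B5.5 condition can never be true for it. A vaccine recipient who leaves the study without fully withdrawing consent has a stated basis for continued safety collection. An Arm 3 participant who leaves in the same way does not. The difference comes from a written rule, not from chance loss to follow-up.

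Arm 3 is the only group that shows the antimalarials without the vaccine. The primary objective is safety with and without concurrent antimalarials. If SAEs are sought for longer after withdrawal in the vaccine arms than in Arm 3, the by-group percentages in the safety table do not rest on the same observation. A faulty analysis-set definition can still be corrected before database lock, whereas SAEs that were never collected cannot be recovered then.

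**Working it through.** **1. What each provision covers** (protocol B5.5; B6.4.7; Tables 5 and 6)

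| Situation | Vaccine recipients (Arms 1, 2) | Arm 3 |
|---|---|---|
| Stops study agent, stays in the study | Scheduled visits through Month 6 | The same |
| Leaves the study because of an AE | That event followed until it settles; long-term collection as appropriate | That event followed until it settles; nothing stated for new SAEs |
| Leaves for another reason, consent not fully withdrawn | Contact attempts if visits are missed; long-term collection as appropriate | Contact attempts if visits are missed |
| Withdraws consent completely | None | None |

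The arms differ only in the two middle rows, and what is missing there is the collection of new SAEs after study withdrawal.

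**2. Is Arm 3 part of the endpoint?** The each-group wording (B6.3.1, SAP 3.2) and the No Vaccine column say yes. The safety-set wording (B6.7.2, B6.7.4, SAP 3.1, 4.1.4 and 5) and the first-vaccination clock exclude it or leave it undefined. The documents conflict, so B5.5 cannot be repaired alone: Arm 3 data could be collected and then dropped.

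**3. Effect of censoring.** SAP 3.1 censors losses at the date last seen, but the safety table reports n (%) with a confidence interval. A simple percentage does not use a censoring time. Unless the denominator is changed, an unfollowed participant counts as event-free.

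**4. Size.** The plan states no safety figure to reproduce. Its power for Arm 1 v Arm 2 (85%; 50% v 80%, 50 per arm) reproduces as 85.3% by full enumeration of the two-sided Fisher test, and this point does not affect it.

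- Weight of one Arm 3 participant: 1/20 = 5 percentage points.
- Schedule (Table 7): 28 + 28 + 28 + 84 = 168 days. Someone who leaves at Day 28 has 140 days left, and 140/168 = 83% of that person's follow-up.
- Exact two-sided 95% upper limit with 0 SAEs, 1 − 0.025^(1/n): n=20, 16.8%; n=19, 17.6%; n=18, 18.5%; n=16, 20.6%.
- One unseen SAE: a true 1/20 (5%, exact 95% CI 0.1% to 24.9%) would be reported as 0/20 (0% to 16.8%).

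The documents give no dropout rate, so three values (d) are assumed:

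| d | Expected Arm 3 withdrawals, 20d | P(at least one), 1 − (1 − d)^20 | Arm 3 person-time lost if all leave at Month 1, d × 140/168 | At Month 3, d × 84/168 |
|---|---|---|---|---|
| 5% | 1 | 64% | 4.2% | 2.5% |
| 10% | 2 | 88% | 8.3% | 5.0% |
| 20% | 4 | 99% | 16.7% | 10.0% |

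These are upper bounds on the effect of the clause, because anyone who withdraws consent completely is lost under any wording.

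**The case against.** The strongest reply is that the gap is narrow.

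- **Stopping tablets does not end follow-up.** A reader might infer that an Arm 3 participant who discontinues antimalarials is no longer followed. The documents do not support that. B5.5 separates stopping the agent from leaving the study, the individual stopping rules in Appendix B 1.7 concern further dosing only, and Tables 5 and 6 keep AE assessment for Group 3 at Months 3 and 6. This stands and confines the point to study withdrawal.
- **Withdrawn participants are not simply abandoned.** AE withdrawals are followed until the event settles, and non-returners are contacted in all arms. This stands, but neither provision commits the site to seeking new SAEs through Month 6.
- **The vaccine arms are not guaranteed complete data.** B5.5 promises collection only as appropriate and names no Month 6 contact. Consent withdrawal and loss to follow-up can occur in any arm. It would be wrong to read the plan as having no comparable loss in Arms 1 and 2.
- **No direction of bias is shown.** It is tempting to conclude that drugs alone will look safer because those who tolerated them poorly drop out. Those are mostly AE withdrawals, whose events are followed. Nothing in the documents shows that the remaining withdrawals are selected for intolerance. No Arm 1 v Arm 3 safety test is specified either; the analysis is descriptive by group.
- **The documents may not intend Arm 3 to be in the safety set.** Several passages say so, but others say the opposite, and the conflict itself needs settling.

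Replacement of withdrawals (B5.3) adds a participant but does not recover the events of the one who left.

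**Conclusion.** The point holds in a limited form. B5.5 makes long-term safety collection after withdrawal conditional on a vaccine dose, which Arm 3 cannot meet. For that arm nothing provides for new SAEs after study withdrawal, beyond follow-up of the causative event and contact attempts. Whole-period SAE ascertainment may therefore differ by arm for an endpoint stated for each group.

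The documents do not support saying that the Arm 3 endpoint is incomplete, or that it is biased in a known direction. Either would require at least one Arm 3 withdrawal short of complete consent withdrawal, and bias would also require missed events. With 0 SAEs and two such withdrawals assumed, the upper limit moves from 16.8% to 18.5%, a difference of 1.7 points. A single missed SAE would move the Arm 3 rate by 5 points. Sample size and power are unaffected. The clause is still worth correcting because the asymmetry is written into the rule and is cheap to remove.

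**What to change.** 1. In protocol B5.5, replace the vaccine-dose condition with receipt of at least one dose of any study agent, vaccine or antimalarial. Extend the definition of withdrawal from the study agent to cover antimalarial rounds.
2. State the same SAE contact through Month 6 for withdrawn participants in all three arms, unless consent is fully withdrawn.
3. Reconcile the safety-set wording in protocol B6.7.2 and B6.7.4 and SAP 3.1, 4.1.4 and 5 with the each-group endpoint and the No Vaccine column, so that the Arm 3 data are analysed. Give Arm 3 a start for the six-month window, such as Month 0 / Day 0.
4. In the SAP, state how unfollowed participants enter the denominators of the safety table.

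The cost is a short amendment and a few extra safety contacts. Month 3 and Month 6 visits are already scheduled and compensated for Group 3 (Tables 6 and 10). The change concerns data collection and analysis only, not dosing or care.
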